Alternatives to Participation

1. *Please list other available clinical treatments.*
2. *Please state if a subject could continue on standard of care therapy and what that might include.*
3. *If not a clinical trial you may state that the alternative is not to participate. If there is a viable alternative you must list it in the consent.*

This is an observational study and clinical treatment is not provided. This study is being performed for research purposes only. The alternative to the study is simply not to participate.

Costs to Research Participants

There are no costs to research participants or their insurance companies – *please leave the rest of this section blank*

1. *If applicable, describe what costs the research participants will be responsible for because of participation in the research including but not limited to: transportation to study visits, parking for study visits, costs of procedures, lost, broken or stolen devices, costs of drugs or therapy, etc.*
2. *You must clearly state if insurance will be charged and who will be responsible if insurance does not pay.*
3. *List what research procedures and research interventions will be covered by this study.*

Research Participant Compensation

There is no compensation for research participants – *please leave rest of this section blank*

1. *Describe the schedule, payment method and payment total of any incentives or compensation that research participants will receive for participation in the research (e.g., gift cards or cash with amounts, t-shirts, devices, bags, swag, etc.)*
2. *Describe the schedule, payment method and payment total of any reimbursements that research participants will receive for participation in research (e.g., parking, mileage, meals, etc.)*

As a token of appreciation of the time and effort made by the parent and child to participate in this study, we will compensate each child who completes the protocol with a \$50 Amazon gift card. Each parent whose child completes the protocol and completes the parent questionnaires will also be compensated with a \$50 gift card [note: only one parent per participating child is eligible]. In special circumstances that require a parent proxy to come with the child to the study visit, the study team, parent, and caregiver will make a decision as to who can best respond to the questionnaires about the child’s activities and behaviors. The parent or the caregiver who completes the questionnaire will be compensated \$50. The total compensation for the child/parent unit is \$100 value. If two children participate from the same family (e.g. one healthy child and one former preterm child OR two healthy OR two former preterm children), they will be eligible for \$100 for each participating child/parent

unit. If a child/parent completes the protocol a second time, the child will receive a \$50 Amazon gift card and the parent will receive a \$50 gift card for completing the re-study.

The \$50 parent/caregiver incentive is also meant to cover expenses of parking during the time of data collection. Both the child and the parent/caregiver will receive their incentives on the day of the data collection visit.

Compensation for Research Related Injury

Describe who will pay for the costs of medical treatment and/or compensation in the event of a research related injury:

- Funding agency is providing some/all payment for injury
- Funding agency is providing no payment for injury
- Not applicable

Provisions to Monitor the Data to Ensure the Safety of Research Participants

1. *Describe the Data and Safety Monitoring Plan for the proposed study. Describe how often the data will be monitored for completeness, accuracy and adherence to the protocol.*
2. *Is there a formal Data and Safety Monitoring Board/Committee? If yes, provide information about the DSMB/C including the contact information of the committee member(s) (as applicable); whether it is independent from the study sponsor; how often it meets; the type of data that will be used; written reports, etc.*

Given the minimal risk of the procedures involved in the study the likelihood of adverse events is very low. Overall risk to participants should be similar to that of a clinical MRI scan. Collection of EEG data is non-invasive. The unblinded study coordinator will monitor records and debrief data collection personnel each week to detect adverse events. Data will be reviewed and monitored to ensure that its accuracy, completeness, and collection is in compliance with the protocol. All adverse events will be classified by severity and will be reported to the IRB in accordance with the rules regulating each severity class (expected vs. unexpected; serious vs. other; related vs. unrelated). With consultation of the physician involved in the project ([name]), criteria for urgent medical referrals will also be established. Per NIH policy, we have developed a detailed Data and Safety Monitoring Plan, which has been approved by NINR/NIH. The approved 7-page document is attached. A DSMB has been assembled with 4 members outside the study team in addition to 3 members of the study team ([name], [name], and biostatistician [name]). Data and procedures will be monitored weekly by the study team to ensure compliance with the protocol and integrity of the data. Quarterly written reports to outside DSMB members summarizing study progress and adverse events will be provided by Drs. [name] and [name]. The DSMB will be included in all formal procedures that report adverse events to the oversight University Hospital IRB and identify any need for premature termination of the protocol.

DSMB members will include (1) [name]: Licensed Clinical Psychologist & Professor of Pediatrics, Division of Developmental/Behavioral Pediatrics & Psychology, Rainbow Babies & Children's Hospital, [contact]. [name] will serve as DSMB chairperson; (2) [name]: Assistant Professor of Pediatric Neurology/Staff Pediatric Epileptologist, Rainbow Babies & Children's Hospital, [contact]; (3) [name]: Director, Neonatal Research Programs, UH Cleveland Medical Center, Professor of Pediatrics, CWRU School of Medicine, [contact]; (4) [name], Lead Teaching Assistant, CWRU School of Medicine, Department of Physiology & Biophysics, [contact]. [name] will serve as the DSMB Executive Secretary. [name], UH-based site PI, will be invited to attend any meetings and be provided with interim written DSMB report updates.

Drugs or Devices

There are no drugs or devices being utilized in this research project – *please leave rest of this section blank*

1. *If the research involves drugs or device(s), describe your plans to store, handle, and administer those drugs or device(s) so that they will be used only on research participants and be used only by authorized investigators.*
2. *How will the drug(s) be dispensed (i.e., indicate the pharmacy that will be used)?*
3. *If the drug is investigational (has an IND) or the device has an IDE or a claim of abbreviated IDE (non-significant risk device), identify the holder of the IND/IDE/Abbreviated IDE*

Additional Information

If you have any additional information regarding your study not covered in the template, please include it here.

Community-Based Participatory Research

This is not a community-based participatory research project – *please leave rest of this section blank*

If applicable, describe the involvement of the community in the design and conduct of the research.

Note: Community based research is research that is conducted as an equal partnership between academic investigators and members of a community. In Community Based Participatory Research (CBPR) protects, the community participates fully in all aspects of the research process.

International information

- This is not an international study – *please leave rest of the section blank*
- We will be conducting this research at the following international sites:
 - 1.
- We are recruiting participants outside of the US from the following locations:
 - 1.
- We are sending data outside of the US to the following locations:
 - 1.
- We are receiving data from outside of the US from the following locations:
 - 1.

MULTI-SITE RESEARCH (when UH or CWRU is the IRB of Record)

Does this project have multiple sites?

- Yes
- No

Non-Local Site Information for Multi-Site Studies

If this is a multi-site study where you are the lead investigator, list the following information for each relying site:

1. Name of site:
2. PI of relying site:
3. Name of IRB contact:
4. Phone number of IRB contact:
5. Email address of IRB contact:

Non-Local Recruitment Methods for Multi-Site Studies

If this is a multi-site study and research participants will be recruited by methods not under the control of the local site (e.g. call centers, national advertisements) describe those methods.

Local recruitment methods are described above.

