6.	Child unable to participate in neuroimaging due to claustrophobia or medical contraindication to MRI including any implanted medical device, dental braces, surgical clips for aneurysms in the head, heart valve prostheses, electrodes or other metallic objects; pregnancy
7.	Healthy control children who were treated in the Neonatal ICU during the newborn period for breathing difficulties.
8.	Healthy control children who were hospitalized for breathing problems in the first 3 months of infancy.
9.	If the child is suffering from an acute illness, he or she will be temporarily deferred.

Number of Research Participants

- Indicate the target number of research participants to be accrued locally.*
 Our goal is to obtain 30 complete data sets (preferably Study group = 20; Healthy control = 10). Due to movement artifact in the MRI, some scan data may not be usable so we may need to enroll up to 35 participants. We may also conduct repeat studies on a subset of up to 5 children (~15%) to establish reproducibility of collected data. Only subjects who checked "yes I agree to be contacted..." on their first signed parent consent form will be approached by phone to ascertain interest in participating in the study a second time. Participants studied twice will be re-consented for the second data collection session.
- If this is a multi-site study, indicate the total number of research participants to be accrued across all sites.*
 N/A

Vulnerable Populations

- Indicate specifically if you will include each of the following special populations by checking the appropriate box:*

 - Adults unable to consent**
 - Minors (infants, children, teenagers)**
 - Wards of the state
 - Foster Children
 - Pregnant Women**
 - Neonates**
 - Neonates of Uncertain Viability**
 - Employees of CWRU or UHHS**
 - Prisoners**
 - Illiterate Individuals**
 - Non-English Speaking**
 - University Students**

- If the research involves individuals that are included in a vulnerable population, describe the additional safeguards included to protect the rights and welfare of the individuals for each population indicated.*

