- neurobehavioral assessment results (grooved pegboard test, verbal n-back, Child Behavior Checklist, Vanderbilt Assessment test, Child’s Sleep Habits Questionnaire, Pediatric Sleep Questionnaire)

Covariates include 1) age, 2) sex, 3) race, 4) preterm vs. term birth, and 5) frequency of hypoxic insults (< 5000 versus ≥ 5000) during the first 8 weeks of life within the preterm group. The continuous outcome measure variables will be summarized using descriptive statistics (mean, standard deviation, median, interquartile range). Frequency analyses and stem-n-leaf graphs will characterize data distributions. Skewed continuous variables will be transformed to satisfy normality assumptions of hypothesis testing. Outcome measures for the two groups will be compared graphically using box plots. We will perform hypothesis tests for equality of data distribution for the two groups using t-tests or Wilcoxon sign rank test, as appropriate, with a significance level of 10%.

As we are interested in the differences of above mentioned outcome measures in two groups, we will focus on effect size estimation for the differences of our measures. To detect significant effect size, we will perform regression analysis on the outcomes of interest with the primary covariate of interest being group membership (preterm vs. term birth). In the regression analyses, we will control only for significant confounding effects of age, sex, race, and frequency of hypoxic insults. Using regression analyses, we will determine point

estimates, regression coefficients (beta), as well as 90% confidence interval of betas. The confidence intervals will be main estimated effect size or the differences in outcomes in two groups due to preterm and term birth.

Confidentiality of Specimens and Banking

I am not storing specimens in this research project – *please leave the rest of this section blank*

Describe:

- The source of the specimens*
- Where the specimens will be stored*
- How long the specimens will be stored*
- How the specimens will be labeled*
- How the specimens will be accessed*
- Who will have access to the specimens*
- When and how will the specimens be destroyed*
- How will the specimens be transported (Please note if transporting specimens, a Material Transfer Agreement (MTA) is required).*

Describe:

- The procedures to release specimens including:*
 - i. The process to request a release*
 - ii. Approvals required for a release*
 - iii. Who can obtain specimens*

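### Residual head motion is not accounted for in the FA, ADC and fMRI-BOLD group comparisons, so any group difference in motion can appear in part as a brain difference.

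*Combined protocol and SAP*

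**What the plan says.** Under Number of Research Participants the target is stated as "Our goal is to obtain 30 complete data sets (preferably Study group = 20; Healthy control = 10"), and the allowance for motion follows: "Due to movement artifact in the MRI, some scan data may not be usable", for which enrolment may rise to 35. No loss rate is given, overall or by group.

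Two other steps bear on motion. Study Design, Procedures and Timeline has each child acclimated in a mock scanner before the MRI. Withdrawal of Research Participants removes children who cannot cooperate with the procedures.

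The Data Analysis Plan names ADC and FA from DTI, and BOLD during the n-back, among the outcomes. It compares the groups by t-test or Wilcoxon test at the 10% level, and by regression reporting point estimates "as well as 90% confidence interval of betas". The covariate list reads "Covariates include 1) age, 2) sex, 3) race, 4) preterm vs. term birth, and 5) frequency of hypoxic insults", the last split at 5000 events within the preterm group. On adjustment the plan says "we will control only for significant confounding effects of age, sex, race, and frequency of hypoxic insults".

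No per-child motion measure appears in the List of Data to be Collected or among the covariates. The documents describe no motion correction, no criterion for an unusable scan, no masked review of scan quality and no report of motion or scan loss by group.

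**The concern.** Motion is graded. If its worst form makes a scan unusable, lesser amounts can remain in the scans that are kept. The outcomes at issue (FA, ADC and BOLD) are estimated from those scans. If preterm and term children differ in residual motion, the group coefficient absorbs part of that difference, and a regression confined to the listed covariates cannot separate the two.

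A group difference is plausible but not shown. The Background reports locomotor hyperactivity in the rodent model among features it says are also seen in preterm infants. The section on recruitment materials expects more functional limitations in the preterm group.

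The stake goes beyond a single test. The Data Analysis Plan makes effect-size estimation its focus and intends these 30 children's data to set sample sizes for later studies. A bias here would carry into those calculations.

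**Working it through.** **The plan's own figure.** The only stated number tied to motion is the ceiling of 35. Enrolment for 30 complete sets is 30 / (1 − loss). A loss of 5/35 = 14.3% gives 35, 10% gives 34 and 15% gives 36. So 35 is arithmetically consistent with a loss of that order, but it cannot be reproduced independently because no rate is stated.

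**Inputs from the documents.** 20 preterm and 10 term children; 10% significance level, taken as two-sided to match the 90% interval.

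**Assumed inputs, absent from the documents.** Group difference in motion: 0.3 to 0.8 SD. Within-group correlation of motion with the imaging outcome: 0.2 to 0.5.

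**Precision.** In outcome SD units, SE = √(1/20 + 1/10) = 0.387. With 28 degrees of freedom the critical t is 1.701, so the 90% CI half-width is 1.701 × 0.387 = 0.66 SD.

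**Spurious shift.** Shift = (group difference in motion) × (correlation). The rejection rate with no true brain difference comes from the noncentral t distribution (df 28, noncentrality = shift / 0.387):

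| Motion difference (SD) | Correlation | Shift (SD) | Rejection rate |
|---|---|---|---|
| 0 | any | 0 | 10.0% |
| 0.3 | 0.2 | 0.06 | 10.4% |
| 0.5 | 0.3 | 0.15 | 12.4% |
| 0.55 (midpoint) | 0.35 (midpoint) | 0.19 | 14.0% |
| 0.8 | 0.3 | 0.24 | 16.1% |
| 0.5 | 0.5 | 0.25 | 16.7% |
| 0.8 | 0.5 | 0.40 | 26.6% |

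**Effect of adding motion to the model.** Scenarios with motion differences of 0, 0.5 and 0.8 SD and correlations of 0.3 and 0.5 were simulated, 10,000 runs each. With a motion covariate the rejection rate was 9.8% to 10.2% and the mean spurious coefficient −0.006 to 0.001 SD. The mean 90% half-width was 0.59 to 0.68 SD, against about 0.65 SD without the covariate. This assumes that motion acts linearly and is measured without error.

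**Carry-over to a later study (illustration).** Assume a true effect of 0.5 SD, 80% power, two-sided 5%, and a shift in the same direction as the effect. Then n per group = 2 × (1.96 + 0.842)² / effect² = 15.70 / effect².

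- No shift: 15.70 / 0.50² gives 63 per group.
- Shift 0.06: 15.70 / 0.56² gives 51.
- Shift 0.19 (0.1925 unrounded): 15.70 / 0.6925² gives 33.
- Shift 0.40: 15.70 / 0.90² gives 20.

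A shift in the opposite direction would inflate the planned size or hide a real effect.

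**The case against.** **The plan does more than replace scans.** A reader of the sample-size section alone might infer that re-enrolment is the only response to motion. The documents do not support that. Children are acclimated in a mock scanner and taught the task beforehand, and those who cannot cooperate are withdrawn. Children with autism or claustrophobia, and preterm children with a low developmental index at two years, are excluded. These steps plausibly reduce motion and may narrow the group gap. They do not measure or adjust for what remains.

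**Silence on processing is not proof of no correction.** Image processing is barely described, so routine realignment may be intended. This stands as a caution on size, because realignment could lower the correlations assumed above. Realignment alone would still not put motion into the group model.

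**The evidence for a group difference is thin.** The hyperactivity finding comes from rodents. The Vanderbilt scale is completed for every child, so collecting it does not show that a difference is expected. This stands, and it is why the point is conditional.

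**Adjustment is not neutral.** The Purpose section hypothesises impaired circuits that modulate motor control. If movement is partly a consequence of that impairment, a motion covariate could remove some real effect. This stands, and it argues against making the adjusted model the sole or default analysis.

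**Selection is not a second, additive harm.** A reader might infer that discarding spoiled scans keeps the calmest preterm children and so compounds the bias. Keeping the calmest would shrink the group difference in motion. Selection is a separate matter that a motion covariate does not repair, and the documents give nothing from which to size it.

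**It is a pilot.** Even the largest assumed shift, 0.40 SD, is below the 0.66 SD half-width. That limits the weight of any one test. It does not answer the point about effect sizes carried forward.

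**Conclusion.** The point holds in conditional form. The plan foresees motion and takes steps to limit it, but its closed adjustment list leaves residual motion out of the FA, ADC and BOLD contrasts. If the groups differ in motion, some of that difference can be read as a brain difference.

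The size rests entirely on assumed inputs. Across the assumed range the nominal 10% error rate becomes anything from practically unchanged to about 27%, with 14.0% at the midpoints. A reader might take the top of the range as the expected false-positive rate, or conclude that the imaging results will be biased. Neither follows, because the documents contain no motion data by group and the bias is nil if the groups move equally.

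This is worth correcting before analysis, since the data needed are already in the scans. It is not a reason to doubt the design as a whole.

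**What to change.** In the Data Analysis Plan:

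- Add a prespecified sensitivity analysis for each DTI and fMRI outcome. It repeats the group regression with each child's mean head displacement, taken from realignment of the existing scans, as a covariate. Present it beside the result without motion.
- Report head motion and the number of scans lost to artifact by group.
- State that scan usability is judged with group masked.

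The cost is one degree of freedom per imaging model and a few sentences of text; no further scanning is needed. The drawback is that adjustment may remove some real effect if movement is itself a consequence of the impairment, which is why both results are shown. Reporting scan loss by group makes selection visible but does not correct it.

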4. Describe when research procedures will take place and the duration of an individual subject's participation in the study. Use of the descriptive table listing the study procedures that indicates the visit/week of the interventions below is encouraged.

	Pre-Screening	Visit 1	Visit 2	Visit 3	Six week Follow up
Estimated time requirement					
Data Collection	X				
Study Procedure 1		X	X	X	
Study Procedure 2		X		X	
Study Procedure 3		X		X	
Phone Call Questionnaire					x

DESIGN & DESCRIPTION: The investigators will conduct an observational study comparing two groups of children to determine whether differences in birth events and oxygen levels during the newborn period lead to structural and functional impairment within the brain's dopaminergic pathways and the cortical regions innervated by those pathways. The dopaminergic system is involved in modulating motor control and cognitive function.

Our goal is to characterize **structure** and **function** of dopaminergic pathways and the cortical regions innervated by those pathways in post-hypoxic former preterm children. We will accomplish this through the use of neuroimaging analysis techniques, such as

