- Health plan beneficiary number
- Account number
- Certificate/license number
- Any vehicle or other device serial
- Device identifiers or serial numbers
- Web URL
- Internet protocol (IP) address
- Finger or voice prints
- Photographic images
- Other: Any characteristic that would uniquely identify the individual

2. *List all other data to be collected for the research study (e.g. laboratory values, physician notes, length of stay, etc.).*

- Magnetic Resonance Imaging, specifically T1 structural scan, Diffusion Tensor Imaging (DTI), and functional Magnetic Resonance Imaging-Blood Oxygen Level Dependent (fMRI-BOLD)
- High density electroencephalography (HD-EEG)

- Neurobehavioral Assessments of child: Verbal n-back; Grooved Pegboard task
Parent report of child behavior (parent-report): Child Behavior Checklist, Vanderbilt Assessment Test, Child’s Sleep Habits Questionnaire (for children ages 9-12), Pediatric Sleep Questionnaire (for children ages 9-17).
- Urine collection (to determine pregnancy exclusion for female child participants)

Data Analysis Plan

1. Describe the data analysis plan, including any statistical procedures. Provide a power analysis if applicable.
2. If applicable, describe the primary and secondary study endpoints including safety endpoints.

Our intent in this exploratory cross-sectional two-arm pilot study is to develop sufficient Scientific Rigor to support a future study appropriately powered to account for our proposed primary outcome measures and co-variates. Our sample will include 20 prematurely born children who experienced hypoxic insults during postnatal life. To allow comparison to “normative” expectations, we will compare these 20 former preterm children with 10 healthy term-born controls without exposure to hypoxia and of similar age, sex, race distribution as the preterm group. Data from these 30 children will be used to develop appropriate sample sizes, using actual rather than predictive data, for future studies characterizing neural structure and function following postnatal hypoxic insults.

Specific structural and functional characteristics used in our analyses will include

- apparent diffusion coefficients and fractional anisotropy generated from DTI data
- fMRI-BOLD, measured during the pediatric verbal n-back, and HD-EEG sLORETA

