1. *Describe the potential benefits that individual research participants may experience from taking part in the research. Include the probability, magnitude, and duration of the potential benefits. Indicate if there is no direct benefit.*
2. *If no direct benefit, state the potential benefit to society or others. Do not list compensation.*

There is no direct benefit to the child by their participation in this research study. Information derived from this study may enable us to determine the underlying neuropathology causing the cognitive dysfunction that can occur following mild-moderate intermittent hypoxic insults in the postnatal period.

Withdrawal of Research Participants

1. *Describe the anticipated circumstances under which research participants will be withdrawn from the research without their consent.*
2. *Describe the procedures that will be followed when research participants withdraw or are withdrawn from the research, including partial withdrawal from procedures with continued data collection.*

A child participant would be removed from this study by the investigators if they cannot cooperate with study procedures or if previously undetected exclusionary criteria become evident during the data collection. These circumstances may include, but may not be limited to: (1) children who cannot cooperate with study procedures such as the ability to perform neurobehavioral tests; (2) if their hairstyle does not permit adequate EEG signal conduction (e.g. dreadlocks are a known problem); (3) if they meet exclusionary criteria such as claustrophobic behavior during the MRI scan or a positive pregnancy test. Data collection will occur in one visit; thus partial withdrawal with continued data collection does not apply to this protocol.

A subject’s participation in this research study is voluntary. Refusing to participate, withdrawing or being withdrawn by study staff will not alter their usual health care or involve any penalty or loss of benefits to which they are otherwise entitled. The images collected are for research purposes only and do not form part of the subject’s routine health care or offer interventions. The images are not a benefit of being in this research study. In the event new information becomes available that may affect the risks or benefits associated with this study or a subject's willingness to participate in it, they will be notified so that they can decide whether or not to continue participating.

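### The preterm-versus-term contrast cannot isolate the oxygen part of the stated purpose, and the plan names no within-preterm analysis that could

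*Combined protocol and SAP*

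**What the plan says.** The design paragraph under Study Design, Procedures and Timeline gives the purpose of the two-group comparison as "to determine whether differences in birth events and oxygen levels during the newborn period lead to structural and functional impairment".

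The Data Analysis Plan defines the groups as "20 prematurely born children who experienced hypoxic insults during postnatal life" and "10 healthy term-born controls without exposure to hypoxia and of similar age, sex, race distribution as the preterm group". The unexposed status of controls is supported by two exclusions under Inclusion and Exclusion Criteria, repeated under Recruitment Methods. One removes "Healthy control children who were treated in the Neonatal ICU during the newborn period for breathing difficulties"; the other removes controls hospitalised for breathing problems in the first three months.

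The regression is described with "the primary covariate of interest being group membership (preterm vs. term birth" status), and the resulting interval is presented as the difference attributable to preterm and term birth. The covariate list opens "Covariates include 1) age, 2) sex, 3) race" and continues with birth group and a two-level count of hypoxic insults (below 5000, or 5000 and above) that exists only within the preterm group. Age, sex, race and this count are adjusted for only where their confounding effect is significant. Gestational age at birth is not listed.

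If the saturation cohort does not supply 20 children, the eligibility and recruitment sections allow preterm children from outside it. The documents do not say how many such children there may be or whether they will have recordings.

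**The concern.** A purpose phrased with a causal verb and naming oxygen levels leads the reader to expect an estimate that speaks to oxygen. The planned main estimate does not. It contrasts children who differ in gestational maturity, in hypoxia and in whatever else accompanies very preterm birth.

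Information on hypoxia apart from prematurity can come only from variation among the preterm children. The plan holds that variation but treats it as a nuisance term that may be screened out. Within the preterm group, gestational age could be related to both event count and outcome, and the plan does not adjust for it.

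The Data Analysis Plan says these data will be used to size later studies of neural structure and function after postnatal hypoxic insults. If a preterm-versus-term difference is carried forward as a hypoxia effect, those studies would be sized on a different quantity.

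**Working it through.** The documents give no power, effect size or standard deviation, so there is no figure to reproduce. The check covers identifiability first and precision second.

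**Inputs.** From the documents: 20 preterm and 10 term children, significance level 10% and 90% intervals (two-sided testing is assumed, to match the intervals). Assumed here: 80% power, the numbers above and below 5000 insults, and the number of children with recordings.

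**1. Can the group contrast separate the two effects?** Code preterm = 1 for 20 children and 0 for 10. As the groups are described, any hypoxia is also 1 for the same 20 and 0 for the same 10.

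- Intercept + preterm + any hypoxia: 3 columns, rank 2. The two effects are aliased.
- Intercept + preterm + low-count + high-count indicators: 4 columns, rank 3. Still aliased.
- Intercept + preterm + high-count indicator, controls coded 0: 3 columns, rank 3. This can be estimated, but the hypoxia coefficient is only the high-minus-low difference among preterm children, and the group coefficient becomes low-count preterm versus term.

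As an illustration, take a total effect of 0.8 SD (assumed) and split it between prematurity and any hypoxia as 0.8/0, 0.4/0.4 or 0/0.8. The expected group difference is 0.8 SD each time. It is also 0.8 SD after adjustment for the high-count indicator. A larger sample would not change this.

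**2. What does the significance screen do to the main estimate?** Suppose 10 of 20 preterm children have 5000 or more insults, and the whole effect is 1.6 SD in those children only. The unadjusted group difference is 1.6 × 10/20 = 0.8 SD. With the indicator in the model, the group coefficient is 0. What the main estimate means therefore depends on whether the term survives the screen. Its standard error, in SD units, also rises from √(1/20 + 1/10) = 0.387 to √(1/10 + 1/10) = 0.447.

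**3. How precise is a within-preterm analysis?** For a continuous event count, by the Fisher approximation with k adjustment covariates:

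detectable |r| = tanh[(1.645 + 0.842) / √(n − 3 − k)]

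| Preterm children with recordings | k | Calculation | Detectable \|r\| |
|---|---|---|---|
| 20 | 0 | tanh(2.487/√17) | 0.54 |
| 20 | 2 | tanh(2.487/√15) | 0.57 |
| 10 (assumed) | 0 | tanh(2.487/√7) | 0.74 |
| 10 (assumed) | 2 | tanh(2.487/√5) | 0.80 |

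For the plan's two-level variable, the two-sample t-test (noncentral t) has these detectable differences: 1.16 SD for 10 versus 10, 1.34 SD for 15 versus 5, and 1.73 SD for 5 versus 5. The main 20 versus 10 contrast detects 0.99 SD.

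**The case against.** The strongest defence is that the plan claims less than its purpose sentence suggests. Much of this stands.

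- The purpose names birth events as well as oxygen levels. Preterm-versus-term does address that composite, so a reader who infers that the contrast fails the whole stated purpose goes too far. Only the oxygen part cannot be isolated.
- A reader might infer that the analysis section presents the group estimate as a hypoxia effect. It does not; it attributes the difference to preterm and term birth.
- A reader might infer that Hypotheses 1 and 2 assert causation by hypoxia. They predict lower values in post-hypoxic former preterm children than in healthy controls. The adjective describes the cohort, and both hypotheses are testable as written.
- The Potential Benefit section mentions the "underlying neuropathology causing the cognitive dysfunction that can occur following mild-moderate intermittent hypoxic insults". That sentence says only that the information may help determine this, and it is not a planned inference.
- The study is described as an exploratory pilot aimed at effect-size estimation, which lowers the stakes.
- The range of gestational age is restricted (22 to 30 weeks, narrower in the primary cohort) and birth weight must be appropriate for gestational age. This limits confounding within the preterm group but does not remove it.

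The aliasing itself is not answered by any of this. No section acknowledges it, and no aim, hypothesis or main estimate names a within-preterm hypoxia contrast.

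**Conclusion.** The concern holds in a limited form. The group contrast estimates preterm birth with its accompanying exposures and cannot show how much of a difference belongs to oxygen. This follows from how the groups are described and does not depend on sample size. The plan's only route to the oxygen question is used as a significance-screened confounder, without gestational age.

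The documents do not support the wider conclusions that the hypotheses are untestable or that the analysis plan mislabels its main estimate.

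A within-preterm analysis would detect only strong associations: |r| of about 0.57 with 20 recordings and two covariates, against an unadjusted best case of 0.54. With 10 recordings the figure is about 0.74 before adjustment. These figures assume a continuous count, two-sided 10% and 80% power. Such an analysis would also remain observational, since other neonatal exposures could still travel with event count. Given pilot status, this is a correction worth making before analysis, not a reason to doubt the study's main comparison.

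**What to change.** 1. Reword the purpose in the Study Design section so that the group contrast is an association with preterm birth and its accompanying exposures. Leave Hypotheses 1 and 2 as comparisons.
2. In the Data Analysis Plan, take hypoxia frequency out of the significance-screened confounders of the group contrast. Name a separate exploratory model among preterm children with saturation recordings, with outcome regressed on event count and adjusted for gestational age at birth and age at scan. Draw any statement about hypoxia only from this model.
3. State the expected precision of that model as above, and report how many preterm children have recordings.

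No new recruitment, visit or measurement is needed. Gestational age is an eligibility item for every child, age is already a covariate, and desaturation events were recorded continuously in the primary cohort. The costs are protocol and SAP wording, one additional model, a narrower headline claim and a less precise hypoxia estimate. Fallback recruits without recordings drop out of the within-preterm model but stay in the group comparison.
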